5.3.1.2 Intended use

These data will be exploratory in nature only

5.3.1.3 Preclinical in vitro and in vivo data, and clinical results

We are not aware of current CyTOF data in the setting of pinometostat treatment

5.3.1.4 Appropriateness

CyTOF is an ideal tool to study simultaneously all hematopoietic and immune subsets in a bone marrow aspirate sample, and this use is well-supported in the scientific literature. CyTOF is capable of detecting shifts in differentiation that are not yet evident by morphology, or conventional flow cytometry. As it is unknown what degree of differentiation may be present after 7 days, the most sensitive assay is favored.

5.3.1.5 Fit for purpose and clinical qualification

See the separate biomarker review committee submission sheet.

5.3.1.6 Collection of Specimen(s)

3.0-5.0 mL of bone marrow aspirate should be collected in a sodium heparin tube.

5.3.1.7 Handling of Specimens(s)

Tubes should be inverted gently at least 3 times.

Tubes may be kept at ambient temperature after collection and during shipment.

5.3.1.8 Shipping of Specimen(s)

Specimens should be shipped by overnight (but not shipped on a Friday or Saturday) express courier to:

Experimental Hematology Laboratory
Attn.: NCI-10212
[name]

[name]
[contact]

5.3.1.9 Site(s) Performing Correlative Study:

LAO-OH007 (Ohio State University)

5.3.2 Studies of Recurrently Mutated Genes by Targeted Capture Panel DNA Sequencing

Upon arrival to OSU, bone marrow blasts from screening, bone marrow at time of count recovery, relapse (if applicable), and off-study (if refractory) aspirate will undergo immunomagnetic selection for CD34+ blasts, which will be snap frozen for later processing. Bone marrow and peripheral blood mononuclear cells from day 8 will also be collected with gradient density centrifugation and snap frozen for later processing. At the time of processing, DNA will be isolated in the standard fashion. If there is evidence of differentiation from other correlative studies, DNA from the day 8 PBMCs will also be prepared for evaluation of mutation variant allele frequency in blasts and non-blasts. We will use the Kapa HyperPLUS prep kit including enzymatic fragmentation and then ligate custom Illumina compatible forked adapters featuring both UMI and 2-sided non-redundant 96x96 sample indexing to the fragmented DNA. Indexed DNA will then be pooled and a custom panel of IDT xGen lockdown probes covering the entire coding region of 90 genes relevant to AML will be used to capture DNA. Captured libraries will be sequenced on an Illumina Hiseq 4000 targeting an average per locus depth of > 1000X.

5.3.2.1 Hypothesis and Rationale as it relates to future development

MLL (KMT2A) rearranged acute leukemias are recognized as having fewer driver somatic gene mutations compared to other acute leukemia subtypes^{8,20}, likely because the epigenetic influence of the MLL fusion has sufficient oncogenic activity. However, there are a subset of cases with driver gene alterations, particularly in RAS and STAT pathways. Relapsed and primary refractory (to conventional therapy) patients may be enriched for mutations compared to MLL rearranged patients with less poor outcomes. Understanding the relationship of potential driver mutations present at diagnosis (especially if in small subclones that have expanded at the time of relapse or off-study) will help improve patient selection and maximize patient benefit should development of pinometostat proceed.

Overall, this biomarker study is anticipated to be hypothesis-generating, rather than testing a specific hypothesis and is therefore exploratory.

5.3.2.2 Intended use

Mutation profiles and temporally differential mutation profiles as they relate to outcome will be used to guide effective patient selection and eligibility in future studies of pinometostat to maximize patient benefit by enrolling patients who are most likely to benefit and conversely

guiding patients who are most likely to be refractory to alternative clinical trials, and to assist in the design of alternative combination strategies to overcome resistance

5.3.2.3 Preclinical in vitro and in vivo data, and clinical results

Not applicable

5.3.2.4 Appropriateness

Mutation-profile-directed therapy is supplanting the all-comers approach to oncology drug development, even in the early phase setting. Collection of this data is a necessary prerequisite to future rational development of pinometostat in the context of AML.

5.3.2.5 Fit for purpose and clinical qualification

The OSU Experimental Hematology Lab targeted AML panel has been deployed in the context of numerous published studies. See supplementary appendices.

5.3.2.6 Collection of Specimen(s)

4.0 mL of bone marrow aspirate should be collected in a sodium heparin tube.

6.0 mL of peripheral blood should be collected in an ACD-A tube.

5.3.2.7 Handling of Specimens(s)

Tubes should be inverted gently at least 3 times.

Tubes may be kept at ambient temperature after collection and during shipment.

5.3.2.8 Shipping of Specimen(s)

Specimens should be shipped by overnight (but not shipped on a Friday or Saturday) express courier to:

Experimental Hematology Laboratory
Attn.: NCI-10212
[name]
[name]
[contact]

5.3.2.9 Site(s) Performing Correlative Study

LAO-OH007 (Ohio State University)

6. TREATMENT PLAN

6.1 Agent Administration

Treatment will be administered on an inpatient basis. Reported adverse events and potential risks are described in Section 10. Appropriate dose modifications are described in Section 6. No investigational or commercial agents or therapies other than those described below may be administered with the intent to treat the patient's malignancy.

A second induction (“reinduction”), if necessary, may be administered and is described in separate table below.

6.1.1 Phase 1b - Safety-Run in Phase

| Regimen Description - Cohort 1 | | | | | |
|--------------------------------|--|---|---|--------------------------------|----------------------|
| Agent | Premedications; Precautions | Dose | Route | Schedule | Cycle Length |
| Pinometostat | Premedications: ondansetron, dexamethasone | 90 mg/m ² /day in NS to a final concentration between 0.54 mg/ml and 5.63 mg/ml | Continuous IV infusion | Days 1-7, week 1 | 35 days (5 weeks) |
| Pinometostat | Premedications: ondansetron, dexamethasone | 60 mg/m ² /day in NS to a final concentration between 0.54 mg/ml and 5.63 mg/ml | Continuous IV infusion | Days 8-35, weeks 2-5 | |
| Daunorubicin (as “7+3”) | Premedications: ondansetron, dexamethasone | 60 mg/m ² in 50-100 mL NS | IV over 10-30 minutes | Daily, days 8-10 | |
| Cytarabine (as “7+3”) | Premedications: ondansetron, dexamethasone | 100 mg/m ² /day in 1,000 mL NS (per day) | Continuous IV infusion at rate to achieve 100mg/m ² in 24 hours | Days 8-14, week 2 | |

| Regimen Description - Cohort 2 | | | | | |
|--------------------------------|--------------------------------|---------------------------|------------|------------|--------------|
| Agent | Premedications; Precautions | Dose | Route | Schedule | Cycle Length |
| Pinometostat | Premedications: | 90 mg/m ² /day | Continuous | Days 1-35, | 35 days |

| | | | | | |
|----------------------------|--|--|--|-------------------|-----------|
| | ondansetron, dexamethasone | in NS to a final concentration between 0.54 mg/ml and 5.63 mg/ml | IV infusion | weeks 1-5 | (5 weeks) |
| Daunorubicin (as "7+3") | Premedications: ondansetron, dexamethasone | 60 mg/m ² in 50-100 mL NS | IV over 10-30 minutes | Daily, days 8-10 | |
| Cytarabine (as "7+3") | Premedications: ondansetron, dexamethasone | 100 mg/m ² /day in 1,000 mL NS (per day) | Continuous IV infusion at rate to achieve 100mg/m ² in 24 hours | Days 8-14, week 2 | |

6.1.2 Phase 2 - Expansion Phase

| Regimen Description | | | | | |
|----------------------------|--|--|--|----------------------|----------------------|
| Agent | Premedications ; Precautions | Dose | Route | Schedule | Cycle Length |
| Pinometostat | Premedications: ondansetron, dexamethasone | Maximum tolerated dose schedule from either Cohort 1 or Cohort 2 from Phase 1b above | Continuous IV infusion | Days 1-35, weeks 1-5 | 35 days (5 weeks) |
| Daunorubicin (as "7+3") | Premedications: ondansetron, dexamethasone | 60 mg/m ² in 50-100 mL NS | IV over 10-30 minutes | Daily, days 8-10 | |
| Cytarabine (as "7+3") | Premedications: ondansetron, dexamethasone | 100 mg/m ² /day in 1,000 mL NS (per day) | Continuous IV infusion at rate to achieve 100mg/m ² in 24 hours | Days 8-14, week 2 | |

6.1.3 Re-induction in either Safety Run-in Phase or Expansion Phase

If a patient in either phase (Phase 1b Safety Run-in, or Phase 2 Expansion) requires re-induction due to not achieving a CR/CRi, they will be treated according to the following schedule. Day numbers below refer to a reset calendar where day 1 refers to the first day of re-induction chemotherapy. The study treatment then continues for a total of 28 days.

| Regimen Description | | | | | |
|-------------------------|--|---|--|----------------------|-------------------|
| Agent | Premedications ; Precautions | Dose | Route | Schedule | Cycle Length |
| Pinometostat | Premedications: ondansetron, dexamethasone | 90 mg/m ² /day, unless 60 mg/m²/day has been previously identified as the maximum tolerated dose after completion of the Safety Run-in Phase | Continuous IV infusion | Days 1-28, weeks 1-4 | 28 days (4 weeks) |
| Daunorubicin (as "5+2") | Premedications: ondansetron, dexamethasone | 60 mg/m ² in 50-100 mL NS | IV over 10-30 minutes | Daily, days 1, 2 | |
| Cytarabine (as "5+2") | Premedications: ondansetron, dexamethasone | 100 mg/m ² /day in 1,000 mL NS (per day) | Continuous IV infusion at rate to achieve 100mg/m ² in 24 hours | Days 1-5 | |

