6.2 Definition of Dose-Limiting Toxicity

DLT Period. DLTs will be evaluated only in the Phase 1b – Safety Run-in Period. The period defined for evaluation of DLT is from the first day of pinometostat administration (day 1) to day 42 after induction, or if a re-induction was attempted, day 42 after re-induction.

Non Hematologic DLT will be determined based on non-hematologic Grade ≥ 3 toxicity related to the study drug alone or the study drug in combination with chemotherapy that occurs within first cycle of the combination. Severity of AEs will be graded according to National Cancer Institute Common Terminology Criteria for Adverse Events (CTCAE) v5. **With the following exceptions:** Grade 3 fatigue < 7 days; correctable electrolyte abnormalities within 72 hours; isolated, asymptomatic AST or ALT (<Grade 4) in the absence of significant bilirubin elevation (<Grade 3) that resolves within 7 days of drug hold; isolated, asymptomatic amylase elevation (<Grade 4) in the absence of lipase elevation (<Grade 3) that resolves within 7 days of drug hold. Pinometostat may be re-initiated in these patients at 60 mg/m² (no matter whether the patient was receiving 90 mg/m² or 60 mg/m²), and re-escalated (if patient was previously on 90 mg/m²; otherwise not applicable) if it does not recur; Grade 3 diarrhea that resolved to \leq Grade 1 or baseline in a week after receiving the maximal supportive therapy based on standard practice Grade 3 nausea and/ or vomiting (excluding need for TPN) that resolved to \leq Grade 1 or baseline in a week after the use of an optimal antiemetic regimen based on standard practice.

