Dose escalation will be performed in the usual 3+3 fashion. See Figure 2. Briefly, 3 patients will be enrolled on cohort 1. If zero of three patients experience dose-limiting toxicities (DLT), proceed to enroll cohort 2. If one of three patients experience DLT, enroll an additional three patients for a total of six patients on cohort 1. If still only one of six total patients experience DLT, proceed to enroll cohort 2. If 2 or more (of either three total or six total patients) experience DLT, accrual will be stopped and a safety review and consideration of further dose level reductions will be discussed between PI, CTEP, and stakeholders. Cohort 2 will be evaluated likewise, except that no further dose level increases will be made, and if toxicity is unacceptable in cohort 2, the dosing plan for cohort 1 will move forward into the expansion phase. Otherwise, the dosing plan for cohort 2 will move forward into phase II expansion.

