7. DOSING DELAYS/DOSE MODIFICATIONS

No intra-patient adjustment of chemotherapy doses is permitted. No intra-patient escalation of study drug is permitted, except as outlined below and with permission of principal investigator. Dose reduction of pinometostat should occur for grade 3 toxicities possibly related to this agent,

excluding hematologic toxicities and select other toxicities that can occur in the phase 2 expansion portion of the study. These select other toxicities for which a dose adjustment is not required include nausea, vomiting, or diarrhea that is manageable without parenteral or enteral feeding; electrolyte abnormalities that are correctable within 48 hours; and grade 3 infections which are expected in this population.

Daunorubicin and cytarabine are only rarely held during the seven-day intensive induction therapy for AML. Dose modifications to daunorubicin or cytarabine are not recommended for treatment-emergent adverse events, and should be discussed with the principal investigator. For patients with a total bilirubin between 1 and 1.5xULN, the daunorubicin dose may be decreased by 75% after discussion with the principal investigator.

| Event | Management/Next Dose for Pinometostat |
|---------------------|--|
| ≤ Grade 1 | Full dose |
| Grade 2 | Full dose |
| Grade 3 | Hold until recovery of < grade 3, then re-initiate with a one-third dose reduction. For example, if the dose was 90 mg/m ² /day, re-initiate at 60 mg/m ² /day. If the dose was 60 mg/m ² /day, re-initiate at 40 mg/m ² /day. If toxicity reoccurs, therapy should be discontinued. See exceptions in section 6, Dose Limiting Toxicities |
| Grade 4 | Discontinue therapy permanently. |

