9. STATISTICAL CONSIDERATIONS

9.1 Study Design/Endpoints

This study is a multi-site phase 1b/2 study designed to confirm a safe and tolerable dose of pinometostat and to gauge preliminary evidence of efficacy when given as lead-in prior to and contemporaneous with standard intensive induction therapy for newly diagnosed AML with MLL rearrangement. The study design involves a brief safety run-in phase exploring two dosing

schemes, followed by a phase II efficacy expansion. The phase II expansion will use the higher dose-level of the two schedules if tolerated (see definitions below), otherwise, the lower dose-level if tolerated. The phase 1b/safety run-in portion will have a primary endpoint of dose limiting toxicity, while the phase 2 portion will have a primary endpoint of complete remission / complete remission with incomplete count recovery attainment, and will gather additional laboratory correlative data.

The phase 1b safety run-in phase involves dividing patients into two cohorts (cohort 1 and cohort 2) after appropriate screening. The goal will be to identify a maximum tolerated dose for expansion. Dose escalation will occur in the standard cohorts-of-3/3+3 design, which is described below. Cohort 1 will comprise of 3-6 patients and will be treated with pinometostat 90 mg/m² continuous IV infusion (CIVI) on days 1-7, then decrease dose to 60 mg/m² CIVI for days 8-35, along with daunorubicin 60 mg/m² daily on days 8-10 and cytarabine 100 mg/m² CIVI on days 8-14. Cohort 2 will comprise of 3-6 patients and will be treated with pinometostat 90 mg/m² CIVI on days 1-35, along with daunorubicin 60 mg/m² daily on days 8-10 and cytarabine 100 mg/m² CIVI on days 8-14.

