Safety and tolerability evaluation and dose escalation for phase 1b will be performed in the usual 3+3 fashion. See Figure 1. Briefly, 3 patients will be enrolled on cohort 1. If zero of three patients experience dose-limiting toxicities (DLT) on pinometostat, proceed to enroll cohort 2. If one of three patients experience DLT, enroll an additional three patients for a total of six patients on cohort 1. If still only one of six total patients experience DLT, proceed to enroll cohort 2. If 2 or more (of either three total or six total patients) experience DLT, accrual will be stopped and a safety review and consideration of further dose level reductions will be discussed between PI, CTEP, and stakeholders. Cohort 2 will be evaluated likewise, except that no further dose level increases of pinometostat will be made, and if toxicity is unacceptable in cohort 2, the dosing plan of pinometostat for cohort 1 will move forward into the expansion phase. Otherwise, the dosing plan for cohort 2 will move forward into phase II expansion. The highest dose of pinometostat that is tolerated as described here will be considered the maximally tolerated dose (MTD).

[figure not shown]

Figure 1. A standard 3+3 dose escalation. With only two cohorts (dose levels), escalation stops

after cohort 2; if 2-3/3 DLT at dose level 1 (cohort 1), a safety review will be initiated to decide whether dose level reductions below the starting dose should be considered.

The phase 2 expansion phase will use the maximum tolerated dose/schedule as determined by phase 1b above and accrue additional patients to gather preliminary evidence of efficacy. Patients will be treated in the same manner as in the phase 1b portion above, with the exception that only a single dose level/cohort will be expanded.

The expansion cohort will comprise 4-25 patients who will be treated at the maximum tolerated dose schedule (see below; phase 1b patients who were treated at the MTD will be included in the statistical analysis of efficacy together with phase 2 patients, which in total comprises 10-31 patients).

Patients requiring re-induction, if any, will be treated at the assigned dose of pinometostat. Patients undergoing re-induction treatment will be analyzed jointly with patients not requiring re-induction for analysis of the primary efficacy endpoint, but a subgroup analysis consisting only of patients who did/did not require a second induction may be conducted.

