The primary efficacy objective is to calculate the rate of complete response (CR) or complete response with incomplete count recovery (CRi) after combination treatment and the primary efficacy hypothesis is that the rate of CR will be higher than among historical controls.

H0: The CR rate is $\leq 65\%$

Ha: The CR rate is $\geq 85\%$

We will use a Simon two-stage design (minimax) to test the hypothesis that the CR rate is greater than 65%. Assuming that the true CR rate among those treated is at least 85%, and setting type I and type II error rates to 10% (yielding $\alpha=\beta=0.1$), we will enroll 13 patients in the first stage. If 8 or fewer responses are observed during stage 1, the study will be stopped early. If there are 9 or more responses, an additional 18 patients will be enrolled in stage 2 for a total of 31 patients. At the completion of the second stage, the drug will be declared efficacious and the probability of an unacceptable CR rate $\leq 64\%$ ruled out if at least 24 CRs are observed out of all 31 patients. This design has a 90% power to correctly rule out a CR rate $\leq 65\%$ if the true rate is 85%, with a type 1 error rate of 0.0951.

| | |
|-----------|----|
| N | 31 |
| n1 | 13 |
| r1 | 8 |
| n2 | 18 |
| r2 | 23 |

NOTE: Patients treated at the maximum tolerated dose in the phase 1b portion (3, or 6) will be counted toward the total needed to satisfy the statistical design. This means that possible total accrual ranges for the whole trial are not $[6, 12+31] = [6, 43]$ but $[6, 12 + 31 - 6] = [6, 37]$

For both phases, early response evaluation will occur at day 21 (day 14 of 7+3) with a bone marrow examination, and if $> 5\%$ myeloid blasts are seen, or $\leq 5\%$ myeloid blasts but with an

aberrant immunophenotype matching the pretreatment immunophenotype, a re-induction attempt may be made with 5 and 2 days of cytarabine and daunorubicin, respectively, both medications at the same doses as initial induction. Pinometostat will be given at 90 mg/m², unless 60 mg/m² was previously established as the RP2D, in which case it shall be given at 60 mg/m². The clock will be reset, and pinometostat will be administered for an additional 28 days (unless stopped early for reasons of toxicity, withdrawal from study, or death).

Exploratory pharmacodynamics biomarkers will be collected at screening, at day 8, and at relapse if applicable for both phases (these are described above).

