f. Long-term follow-up for survival should be conducted at least monthly after patient has completed treatment and should include reporting of survival, subsequent therapy, transplant (if performed). This should be done in person if patient is being followed clinically at the treating center, or by telephone otherwise. After 1 year, this can be done every 3 months. After 5 years, further follow-up is not required.

Table 11.2: Treatment plan for re-induction.

| | Wk 1 | Wk 2 | Wk 3 | Wk 4 | Off Study ^c | Long Term Follow-Up ^g |
|---|----------------|----------------|---------|----------------|------------------------|-------------------------------------|
| Pinometostat | A | A | A | A | | |
| Cytarabine | B | | | | | |
| Daunorubicin | C | | | | | |
| Concurrent meds | X | X | X | X | | |
| Physical exam | X | X | X | X | X | |
| Vital signs | X | X | X | X | X | |
| Height and Weight | X | X | X | X | X | |
| Performance status | X | X | X | X | X | |
| CBC w/diff, plts, PT/INR, aPTT | X | X | X | X | X | |
| Serum chemistry ^a | X | X | X | X | X | |
| Echocardiogram/MUGA ^f | X ^f | | | | | |
| Adverse event evaluation | X | X | X | X | | |
| Bone marrow aspiration and biopsy | | X | | X ^d | | |
| Bone marrow metaphase karyotype | | X | | X ^d | | |
| Bone marrow MLL (KMT2A) translocation by FISH | | X | | X ^d | | |
| Immunophenotyping (BM and PB) | | X | | X ^d | | |
| Differentiation analysis | | X ^e | | X ^d | | |
| Comprehensive mutational profile | | X ^e | | X ^d | X | |
| Survival | | | | | | X ^g |

A: Pinometostat: Dose as assigned; weeks 1-4, days 1-28 of a “reset” calendar where day 1 is the start of 5+2 reinduction
 B: Cytarabine: 100 mg/m2 continuous IV infusion; days 1-5 of re-induction
 C: Daunorubicin: 60 mg/m2 IV; daily days 1,2 of re-induction
 a Albumin, alkaline phosphatase, total bilirubin, bicarbonate, BUN, calcium, chloride, creatinine, glucose, uric acid, LDH, phosphorus, potassium, total protein, SGOT [AST], SGPT [ALT], sodium.
 b. Serum pregnancy test (women of childbearing potential).
 c. Off-study evaluation.
 d. At count recovery in week 4 or beyond
 e. Day 8 of week 2, and at relapse (if applicable), and off-study
 f. Echocardiogram or MUGA should demonstrate EF ≥45% before the second induction cycle (“re-induction”) is initiated

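### During the run-in, the re-induction rule raises a Cohort 1 patient from 60 to 90 mg/m²/day with chemotherapy before Cohort 2 can open, and charges at least some resulting DLTs to Cohort 1

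*Combined protocol and SAP*

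**What the plan says.** **Rule A: 90 by default.** Section 6.1.3 covers re-induction in both the run-in and the expansion. It gives pinometostat at 90 mg/m²/day for 28 days with 5+2. The only exception is where 60 mg/m²/day "has been previously identified as the maximum tolerated dose after completion of the Safety Run-in Phase". Section 9.1 agrees: the dose is 90 mg/m² except where 60 mg/m² "was previously established as the RP2D, in which case it shall be given at" 60 mg/m².

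**Rule B: the assigned dose.** Earlier in the same Section 9.1: "Patients requiring re-induction, if any, will be treated at the assigned dose of pinometostat". The re-induction calendar, Table 11.2, has "Dose as assigned; weeks 1-4, days 1-28". Section 7 adds: "No intra-patient escalation of study drug is permitted, except as outlined below and with permission of principal investigator".

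**The cohorts.** Cohort 1 receives 90 mg/m²/day alone on days 1-7, "then decrease dose to 60 mg/m² CIVI for days 8-35", with 7+3 beginning on day 8. Cohort 2 receives 90 throughout days 1-35 and is the first planned use of 90 with chemotherapy.

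**DLT period and gate.** Section 6.2 ends the DLT period at day 42 after induction, "or if a re-induction was attempted, day 42 after re-induction". On escalation it says: "If zero of three patients experience dose-limiting toxicities (DLT), proceed to enroll cohort 2". One DLT in six also allows escalation. Two or more stop accrual and trigger a safety review.

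**The concern.** Sites have two dose rules for the same patient, and following one breaks the other. Under Rule A, a Cohort 1 non-responder receives pinometostat with chemotherapy at a dose the 3+3 design has not yet opened. Toxicity at that dose then enters the count used to judge the lower dose. DLT is the Phase 1b primary endpoint, and Cohort 1's schedule goes into Phase 2 if Cohort 2 proves too toxic. Mixing two dose levels in that count works against the lower one.

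**Working it through.** The plan gives no figure for this point, so the check is mainly a reading of the rules in sequence.

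**1. Can the exception apply to a Cohort 1 patient?**
- 60 can be named the MTD or RP2D only after Cohort 2 has been tried and found too toxic.
- Cohort 2 opens only after Cohort 1 shows 0/3 or 1/6 DLTs (6.2, 9.1).
- A re-induced patient's DLT period runs to day 42 after re-induction, and the re-induction course lasts 28 days. Counting both from re-induction day 1, dosing ends 42 − 28 = 14 days before that patient's evaluation closes. Counting day 42 from any later point widens the gap.

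The whole re-induction course is therefore given before Cohort 1 is evaluated. The exception cannot apply, and Rule A gives 90.

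**2. Size of the dose change (60 and 90 mg/m²/day, 28 days; 6.1.1, 6.1.3)**
- Relative increase: (90 − 60)/60 = 50%.
- Course total: 28 × 90 = 2,520 mg/m² against 28 × 60 = 1,680 mg/m², a difference of 28 × 30 = 840 mg/m².

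**3. Which DLTs at 90 count against Cohort 1? (6.2)**

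| Criterion | Reaches re-induction? |
|---|---|
| Hematologic | Yes; it names the second induction |
| Less than 75% of planned doses | Yes; re-induction days are in the denominator |
| Grade 2+ non-hematologic needing dose reduction or discontinuation | No first-cycle limit stated |
| Grade 3+ non-hematologic | Unclear; tied to the first cycle of the combination |

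Nothing in the plan moves a DLT to the dose level at which it occurred.

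**4. Effect on the 3+3 decision**

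From the documents only the direction follows. One such DLT turns 0/3 into 1/3 (three more patients), or 1/6 into 2/6 (accrual stop and review).

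The rest of this step is illustration on assumed rates. Let *f* be the re-induction share, *p* the DLT risk at the assigned dose, and *a* the added risk at 90 in a re-induced patient.
- Chance of at least one re-induced patient among *n*: 1 − (1 − f)ⁿ. For f = 0.20 to 0.50 this is 0.49 to 0.88 with n = 3, and 0.74 to 0.98 with n = 6.
- Chance of escalating: P(π) = (1 − π)³ + 3π(1 − π)²(1 − π)³, with π = p under the assigned dose and π = p + f·a under Rule A.
- At p = 0.15 and the assigned dose: 0.614 + 0.200 = 0.814.
- Rule A with f = 0.20, a = 0.10: π = 0.17 and P = 0.773. With f = 0.50, a = 0.30: π = 0.30 and P = 0.494.
- Over the same ranges of f and a, p = 0.10 gives 0.906 falling to between 0.871 and 0.600. p = 0.20 gives 0.709 falling to between 0.665 and 0.396.

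**The case against.** The 90 rule appears twice, with an explicit exception, and 6.1.3 is the dedicated dosing table. It may be a deliberate intensification for non-responders, in which case the assigned-dose sentence in 9.1 is the error. Other points on that side:

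- Section 7 lists no escalation exceptions of its own and points back to Section 6, so its silence on re-induction does not prove that 6.1.3 is barred.
- The Table 11.2 footnote could mean the dose assigned by 6.1.3.
- Cohort 1 has already had a week at 90, and 90 with 5+2 is less chemotherapy than Cohort 2's 90 with 7+3.
- The DLT route is narrow. A hematologic DLT requires a marrow clear of leukemia and neutropenia that persists on reassessment by day 56. The 75% criterion counts only doses missed for related or possibly related non-hematologic toxicity.
- Sections 13.1 and 13.3 provide sign-off, monthly calls and two-weekly reviews, and two DLTs lead to a review rather than automatic rejection of the dose.

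Some of this stands. Section 7 and Table 11.2 are supporting evidence only; the firm conflict is inside Section 9.1 and between 9.1 and 6.1.3. The number of affected patients is small, and the direction of the bias is toward caution. But the week at 90 was without chemotherapy, and 90 with 5+2 shortly after 7+3 is still untested in this trial. Oversight does not tell a site which dose to give. If intensification is intended, the plan must still remove the contradiction and say which dose level is charged with the DLTs; it does neither. The Phase 2 amendment required by 13.1 comes after Cohort 1 has been dosed and counted.

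**Conclusion.** The concern holds. For a re-induced Cohort 1 patient the plan contradicts itself. Under 6.1.3 and the later text of 9.1, that patient receives 50% more pinometostat than assigned (+840 mg/m² over 28 days) with chemotherapy, before that combination is open for testing. At least hematologic and 75%-dose DLTs arising there count against Cohort 1. This should be fixed before Cohort 1 enrolls.

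These conclusions rest on the text and need no assumed rates. The number affected lies within Cohort 1's 3 to 6 patients. The effect on the escalation decision has a known direction but no size that the documents can supply; the probabilities shown above depend entirely on assumed inputs. Whether Grade 3 or higher non-hematologic DLTs during re-induction also count is left open by the wording of 6.2.

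**What to change.** Amend the pinometostat cell of the 6.1.3 table and the matching sentence in 9.1 so that re-induction uses the patient's own chemotherapy-phase dose: 60 mg/m²/day in Cohort 1, 90 in Cohort 2, and in Phase 2 the chemotherapy-phase dose of the selected schedule. State the numbers, because Cohort 1's assigned schedule contains both 90 and 60.

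This agrees with the assigned-dose sentence in 9.1 and the natural reading of Table 11.2, and it avoids any escalation under Section 7. Re-induction DLTs then belong to the enrolled cohort, so no separate charging rule is needed. Phase 2 dosing is unchanged.

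The cost is two wording changes and no extra patients. The one downside is that Cohort 1 non-responders do not receive the higher dose at re-induction. The opposite repair, keeping 90 and correcting the other sections, would leave patients exposed to an uncleared combination dose and would need an added rule for charging DLTs.
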